#### 3.2.2 Secondary Study Endpoints

Secondary endpoints will be evaluated by pre- and post-intervention sleep duration, physical activity, sedentary behavior, diet quality, smoking, alcohol use, affective well-being, morning fatigue, evening fatigue, and self- regulation measurements. These secondary endpoints were chosen to gain preliminary evidence of relationships between SASI and sleep duration, MetS risk behaviors, as well as symptoms associated with MetS risk behaviors, and self-regulation. Elucidating these relationships will inform potential pathways through which SASI impacts MetS.

#### 3.2.3 Exploratory Endpoints

Exploratory endpoints are the perceived barriers and facilitators of SASI. These will be identified through bivariate correlations between specific socio-ecological factors associated with sleep duration changes. Qualitative data analysis from the post intervention interviews will be conducted. Identifying perceived barriers and facilitators will lead to future tailoring and/or targeting of SASI.

## 4 Study Enrollment and Withdrawal

To reach a final sample of N= 60, we will recruit 220 individuals. Of these, we anticipate that 65% will become ineligible through the multi-stage screening process and 20% will be lost to attrition during the intervention leaving 60 participants with evaluable data.

#### 4.2 Exclusion Criteria

An individual who meets any of the following criteria will be excluded from participation in this study:

- 1. Pregnancy/lactation (self-reported). Pregnancy and lactation can disrupt habitual sleep patterns, and hormonal changes during pregnancy increase insulin resistance and may confound MetS.
- Current chemotherapy treatments (self-reported). Current chemotherapy treatments may contribute to fatigue and sleep disturbances.
- Alcohol abuse will be assessed with the Alcohol Use Disorders Identification Test (a measure that has demonstrated good reliability and validity). Alcohol abuse/dependence may contribute to sleep disturbances and limit the participant's ability to take part in sleep interventions. Individuals with scores > 15 (men) or > 13 (women) will be excluded.
- 4. Night shift or shift work (previous 2 months), trans-meridian travel (previous 4 weeks), or planned shift work or trans-meridian travel during intervention period (self-reported). These will be to ensure that sleep estimates from baseline represent participants' habitual sleep and to ensure adherence with the sleep intervention.
- 5. Moderate-severe or severe depression will be assessed with the Patient Health Questionnaire (PHQ-9). The PHQ-9 is reliable and has been shown to have construct and criterion validity (Kroenke et al, 2001). Using professional interviews as the criterion standard, a PHQ-9 score of 10 had a sensitivity of 88% and a specificity of 88% for detecting major depression. It has been validated in clinical populations and been used in a large number of cardiovascular studies. Moderate-severe depression or severe depression may contribute to sleep disturbances and interfere with the participant's ability to adhere to the sleep interventions. Therefore, individuals with scores ≥ 15 will be excluded.
- 6. Chronic use of sleep-promoting medications (self-reported) defined as taking a sleep-promoting medication ≥ 3 nights per week. These may interfere with sleep patterns and limit the participant's ability to take part in the sleep interventions.
- 7. Habitual napping, defined as 2 naps per day or > 90 minutes of napping on 3 or more days of the week will be assessed during baseline with accelerometry. This will be to ensure adherence with the sleep intervention.
- 8. Untreated OSA, defined by an apnea hypopnea index (AHI)> 10 using the hypopnea scoring criteria of a 4% or more oxyhemoglobin saturation. This criterion has been used because of its independent association with cardiovascular disease (Punjabi et al 2008, Punjabi et al 2013).
- 9. Any condition that, in opinion of the PI, will interfere with the safe completion of the study.

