## 1 Introduction, Background Information and Scientific Rationale

#### 1.1 Background Information and Relevant Literature

Name and description of the study intervention. The Self-management for Adequate Sleep Intervention (SASI) is a 12-week self-management for adequate sleep intervention (SASI) that extends sleep gradually based on individual responses to the intervention. Participants will be enrolled in the study for 18 weeks because we will be collecting baseline sleep data during weeks 1 and 2, confirming eligibility based on objectively measured sleep and personalizing the intervention during week 3, delivering SASI weeks 4-15, and completing the last study visit within 3 weeks of the last day of the intervention. SASI is based on Cognitive Behavioral Therapy for Insomnia (CBTI). Like CBTI, SASI extends sleep based on sleep efficiency (the proportion of time spent sleeping during a sleep episode). Bed times and wake times will be prescribed each week for each participant and allow for gradual increases in sleep opportunity. Bedtimes will be set 15 minutes earlier each week provided sleep efficiency remains >90%. Earlier bedtimes will extend sleep duration by increasing the opportunity for sleep. Wake times will not be changed because wake times are often determined by external demands, such as work schedules.

Summary of relevant clinical research. Diet and exercise are the first line of treatment for effectively reducing the Metabolic Syndrome (MetS). However, disappointing outcomes are reported when diet and exercise programs are translated into less intense, more affordable community based programs. Less intense programs report only half the amount of weight loss achieved by more intense programs. Moreover, only 50% of Americans with elevated glucose levels attempt modifying their diets and physical activity. Poor participation rates suggest that diet and exercise are only effective for select, highly motivated individuals. Extending sleep is an innovative approach to reducing MetS because it shifts the first line of treatment from diet and exercise alone to include sleep, a potentially modifiable, upstream factor for MetS.

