## 3 Study Design and Endpoints

#### 3.1 Description of Study Design

This single site, one group, pilot study will test the acceptability and feasibility of the Self- management for Adequate Sleep Intervention (SASI) in racially/ethnically diverse middle-aged adults with MetS.

This is an 18-week study. In the first 2 weeks, baseline data will be collected. During week 3, the baseline data will be used to confirm study eligibility based on objectively estimated short sleep and to plan the personalized intervention. During weeks 4 to 15, the study team will call or videoconference participants once a week to prescribe a sleep schedule based on their daily sleep diaries. At the end of week 15, participants will be asked to schedule their final visit within 3 weeks.

Version Date: September 27, 2019

Acceptability data will be collected at two time points (i.e., pre- intervention and at the final visit). The final visit will include a 30-minute open ended interview to explore perceived facilitators and barriers to implementing SASI. The intake visit will take place at the CTSI. The final visit will take place using video conferencing technology such as WebEx. Weekly contact with the study team will take place during the intervention weeks so that SASI can be personalized based on individual responses to the sleep intervention. This weekly contact will be remote in the form of telephone calls or remote video conferencing technology.

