#### Telephone Screening (within 4 weeks of CTSI visit 1)

- Telephone screen administered (Duration: approximately 15 minutes) 

   If eligible and interested, schedule CTSI visit 1 within 4 weeks of the telephone screen
- Figure 1 for Multi-stage Screening and Enrollment Flowchart

Figure 1: Multi-stage Screening and Enrollment Flowchart

Version Date: September 27, 2019

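### The shift-work and travel exclusion is meant to keep baseline sleep habitual, but it does not name the baseline weeks, and no later check is described

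*Combined protocol and SAP*

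**What the plan says.** Criterion 4 in Section 4.2 combines two look-backs with one look-ahead. It bars anyone with night or other shift work in the past 2 months, and then names "trans-meridian travel (previous 4 weeks), or planned shift work or trans-meridian travel during intervention period (self-reported". Its first stated reason is "to ensure that sleep estimates from baseline represent participants' habitual sleep"; the second is adherence to the intervention. No date is given from which the look-backs are counted.

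Section 3.1 sets the calendar. On baseline it says "In the first 2 weeks, baseline data will be collected". Week 3 is for confirming eligibility and planning, and then "During weeks 4 to 15, the study team will call or videoconference participants once a week". Section 1.1 agrees: "delivering SASI weeks 4-15". Under Telephone Screening, staff are to "schedule CTSI visit 1 within 4 weeks of the telephone screen".

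The baseline fortnight has three uses:
- Section 4.1, criterion 3: short sleep is confirmed by accelerometry as a work-day average of 6 hours or less.
- Section 7.3.3.3 (Week 3): the work-day diary from baseline week 2 is used to set the first bed and wake times.
- Section 12.4.3: the two-week baseline diary is the pre value of sleep duration, the main secondary endpoint, compared by paired t-test with the last two intervention weeks.

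Section 7.3.3.3 retains participants with confirmed MetS, confirmed short sleep and, where relevant, treated OSA. It mentions neither travel nor shift work. Section 4.5.1 lets the investigator end participation when an exclusion criterion newly arises or is newly recognised.

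**The concern.** The criterion says that it protects baseline, but the only future period it names starts in week 4. Someone who reports at screening that they will cross time zones in baseline week 1 and be home before week 4 meets no exclusion at that moment. The same holds for shift work that starts and ends before week 4. Criterion 7 (napping) shows the contrast, because it is expressly assessed during baseline.

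The stake is selection as well as noise. Travel or shift work may lengthen or shorten sleep, but a cut at 6 hours admits those in whom it was shortened. When their ordinary sleep returns, the change counts as improvement. This is a one-group study whose data are meant to inform a randomized trial (Sections 1.1 and 1.2), so nothing in the design separates that recovery from an effect of SASI.

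**Working it through.** **Plan's own figure.** The plan gives no number on this point. Its only sample-size figure, 220 screened for 60 evaluable (Section 12.5), reproduces: 220 × (1 − 0.65) × (1 − 0.20) = 61.6. It plays no part below.

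**1. Windows.** Take Visit 1 as the start of week 1 (assumption).
- Baseline, weeks 1-2: 14 days. Week 3: 7 days. The look-ahead starts in week 4.
- If the question is asked at Visit 1, the look-ahead misses 14 + 7 = 21 days, including all 14 baseline days.
- If it is asked only at the telephone screen, up to 28 + 21 = 49 days are missed. Only 14 of these feed the data directly.
- If it were asked at the start of week 3, the 4-week travel look-back (28 days) and the 2-month shift-work look-back would both cover the 14 baseline days. No document describes asking then.

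**2. One participant (nights and hours assumed).** Two weeks hold about 5 × 2 = 10 work nights. The fall in the work-day mean is nights affected × hours lost / 10.
- 2 × 1 / 10 = 0.2 h
- 3 × 2 / 10 = 0.6 h, so a habitual 6.5 h sleeper measures 5.9 h and qualifies
- 5 × 2 / 10 = 1.0 h

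If the diary shows the same weekday loss, the 5:2 weighting in Section 12.4.3 turns 0.6 h into 0.6 × 5/7 = 0.43 h in that person's pre value.

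**3. Group mean before selection (assumed).** If a share f is affected and mean baseline sleep falls by d minutes, the spurious gain is f × d.

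| f | d = 30 min | d = 60 min |
|---|---|---|
| 5% | 1.5 min | 3 min |
| 10% | 3 min | 6 min |
| 20% | 6 min | 12 min |

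**4. Effect of the 6-hour cut (simulation, all inputs assumed).** Habitual work-day sleep had mean 6.0 or 6.5 h and SD 0.8 h; two-week measurement error had SD 0.3 h; 10% were disrupted by 30 or 60 minutes; one instrument served both uses.
- The disrupted 10% became 14-22% of those who qualified.
- Between 4% and 14% of qualifiers qualified only because of the disruption.
- With no intervention effect, the apparent gain rose from about 5-8 minutes (regression to the mean alone) to about 9-20 minutes.
- The added part was 8.9 − 5.0 = 3.9 and 12.2 − 7.6 = 4.6 minutes for a 30-minute disruption, against f × d = 3. It was 14.2 − 5.1 = 9.1 and 19.9 − 7.6 = 12.3 minutes for 60 minutes, against f × d = 6.

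So the cut enlarges the simple f × d figure. Using one instrument for both purposes makes the link tighter than in the trial.

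**The case against.** The best defence is that the look-backs have no anchor date. The schematic treats the two-week baseline as part of screening, and eligibility is settled in week 3. Counted from then, the look-backs cover baseline, and Section 4.5.1 would let the investigator act. This stands as a possible reading. But the protocol tells nobody to ask in week 3, and the power in Section 4.5.1 is discretionary.

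Several stronger readings are tempting but not supported:
- *Any new shift work in baseline escapes.* It does not. Shift work planned to continue into week 4 is already excluded; only work that ends before then is missed.
- *Seven weeks are unprotected.* That is the upper bound, for a question asked only by telephone. Week 3 supplies no baseline measurement, and the weeks before Visit 1 matter only through carry-over.
- *The question is never asked.* The telephone script and the screening flowchart cannot be seen, and Table 2 counts 10 general health questions while Section 6.1.1 lists at most nine items. What can be said is that no re-check is described.
- *One distorted number is both entry criterion and pre value.* Eligibility uses work-day accelerometry; the endpoint uses a diary mean weighted over weekdays and weekends. They share the fortnight, not the instrument. Disruption confined to non-work days would touch only the diary.

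The protocol's labels for the intervention also vary: Attachment A starts it in week 3, and a survey heading in Section 6.1.1 says weeks 1-15. The design text in Sections 1.1, 3.1 and 4.5 consistently gives weeks 4-15.

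Finally, Section 12.2 disclaims inference to the wider population and Section 12.4.7.2 says that efficacy is not evaluated. This limits the importance of the point. It does not remove it, because preliminary efficacy on sleep duration is a stated secondary objective.

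**Conclusion.** The concern holds in limited form. The criterion's look-ahead covers the wrong window for its stated purpose, its look-backs are unanchored, and no described step catches travel, or shift work that ends before week 4, during baseline. Short sleep caused by such disruption can therefore qualify a participant and lower the pre value.

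The size is unknown, because the documents give no frequency of travel or shift change and no typical sleep loss. The assumed range of 1.5-12 minutes shows scale only. A reader might infer that an observed sleep gain would be largely artefact; nothing in the documents supports that. The acceptability, attrition and diary-adherence endpoints are not directly affected. The point bears on eligibility, the starting schedule and the main secondary comparison, and is worth correcting because the correction is cheap.

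**What to change.** Reword criterion 4 so that both look-backs are counted from the start of baseline and the look-ahead runs from the start of baseline through the end of the intervention (week 15). Re-ask the question at Visit 1, which covers the up to four weeks since the telephone screen, and at the existing week-3 eligibility contact, which covers baseline itself.

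State in advance what follows from a positive answer. If the travel or shift work is known beforehand, schedule baseline after it. If it is found at week 3, apply the exclusion or do not confirm short sleep from the affected nights, and say whether those nights also leave the diary baseline.

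The cost is one reworded sentence and one question at two existing contacts, with an occasional delayed start or extra screen failure. Repeating a baseline would add two weeks of devices and diaries beyond the stated 18 weeks, so scheduling around known travel is the lighter option. The target of 60 does not change.

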#### 4.3 Vulnerable Subjects

No special classes of people who may be considered vulnerable populations (e.g., fetuses, neonates, pregnant women, children less than 16 years of age, prisoners, institutionalized individuals) will be recruited into the study.

#### 4.4 Strategies for Recruitment and Retention

Recruitment. Recruitment strategies will include 1) electronically posting IRB-approved flyers at NYULH, NYU College of Dentistry, NYU College of Nursing, Seastreak commuter ferries and ferry terminals, and metro terminals, 2) advertising in the community so interested individuals can contact the study team, 3) posting/distributing IRB-approved flyers in the community and in clinics, 4) contacting Co-l's past study participants who agreed to be contacted for future research studies, 5) using Epic to identify potential participants (see section below on using DataCore for recruitment/identification purposes, and 6) sending IRB-approved study recruitment messages to potential study volunteers using research registries such as Research Match. Subject identification and recruitment are described in detail below.

Version Date: September 27, 2019

Retention. We will offer an incentive for completing each of the study visits, as well as for completing 6 weeks of the SASI intervention (Total incentive: \$100). Multiple means of contact will be collected for enrolled participants, including email, mailing address, and phone number. Reminders for study visits will be sent via email, if available, or via one of the other means of contact.

#### 4.4.1 Electronically-posted flyers

IRB-approved electronic flyers will be posted at selected sites with permission from the site. Potential sites include NYULH, NYU College of Dentistry, NYU College of Nursing, Seastreak commuter ferries and ferry terminals, and metro terminals. Interested persons responding to the flyers will be contacted by the RA and provided with the option of proceeding with the IRB-approved verbal telephone consent and screening. See study flyer attached with study team contact information.

#### 4.4.2 Advertising in the community

Community members may learn of the study through electronically-posted flyers (see Section 4.4.1), or other methods, such as radio talk shows (e.g. NYU Langone Nurse Radio, sleep apnea support groups). Interested community members may contact the study team for more information about the study. After contacting the study team, the RA will provide individuals with the option of proceeding with the IRB-approved verbal telephone consent and screening.

#### 4.4.3 Posted/distributed flyers

Flyers promoting the study will be available to individuals who visit the participating health facilities (see Section 4.4.4 NYU Langone Health Recruitment for more detailed information). Flyers will also be distributed at community sites so that interested individuals can contact the study team. Those responding to the distributed flyer will be contacted by the RA and provided with the option of proceeding with the IRB-approved verbal telephone consent and screening.

#### 4.4.4 NYU Langone Health recruitment

This study will recruit individuals from settings affiliated with NYU Langone Health, such as employee health, occupational medicine, cardiology, endocrinology, and college of nursing faculty practices. Flyers promoting this study will be available to individuals who visit the participating health facilities or attend employee health events (e.g. flu shot clinics, health fairs). Clinical staff informed of the study protocol and provided with the IRB-approved study information may also inform individuals about the study and refer them to the study team to contact if interested in participating in the study. With approval of the clinic site, the research staff will also be available at the clinic site during specific hours to facilitate recruitment.

#### 4.4.5 Past study participants

Only past study participants from the Co-l's previous studies who agreed to be contacted for future studies will be contacted by the RA. Contacted individuals expressing interest in the study will be provided with the option of proceeding with the IRB-approved verbal telephone consent and screening.

#### 4.4.6 Use of DataCore/Epic Information for Recruitment Purposes

A study team member will submit a request to DataCore to identify potential participants. Data points to be searched will include age, blood pressure measurements, fasting glucose, serum triglycerides, HDL-c, medication use (antihypertensives, insulin, oral hypoglycemic, hypertriglyceridia medication, or medication use for low HDL-c) within the last 6 months. A DataCore query will be run at the start of the study and six months after the study start depending on recruitment rates. DataCore will request a report from EPIC for these patients with identifiable protected health information (name, email address) for research related purposed. Only study team members with Epic access will have access to the search results.

The Epic team will set up a recruitment message in MyChart and work with the PI and project coordinator to send it out. The IRB-approved MyChart recruitment message is attached. The text will include a description of the study, inclusion and exclusion criteria, and contact information for the PI (phone number and email). The recruitment message may be repeated two times at two-month intervals if needed for subject recruitment (total 3 Epic MyChart messages).

These data will be used solely for participant identification in order to determine patients who are initially eligible and for chart review (previous 12-month blood specimen results from Co-investigator's study). The study team will discard information from those who do not wish to participate in the study. If a subject requests information regarding opting out of further recruitment for all research, subjects will be directed to

Version Date: September 27, 2019

contact the study coordinator or have subjects contact research-contact- [contact] or [name].

#### 4.4.7 Research Match

We will also utilize Research Match (ResearchMatch.org), a national, electronic, web-based recruitment tool that was created through the Clinical and Translational Science Awards Consortium in 2009 to send study recruitment messages to potential study participants. This study's recruitment content will be inserted into the standard Research Match electronic notification that informs possible matched participants that they have been identified as a potential match for this study. The Research match recruitment message is attached. The secure Research Match clearinghouse will route this standard Research Match notification to each of these Research Match participants. These potentially matching participants will have the option of replying "yes", "no", or "not respond" through a set of quick links available in this notification of the study announcement. The contact information of the "yes" responding participants will be made available on the PI's "Manage my Study" dashboard. A member of the research team will contact the individual who expresses interest and provide the option for the verbal/telephone consent and screening or an in-person meeting. If a subject requests information regarding opting out of further recruitment for all research, subjects will be directed to contact the study coordinator or have subjects contact [contact] or [name].

